6.3 Lifestyle Restrictions

6.3.1 Alcohol and Tobacco

The following alcohol and tobacco restrictions apply to the phase 1b part of the study only.

At screening and throughout the duration of the study, subjects must not consume > 1 drink of alcohol per day and no more than 3 drinks per week, where a drink is equivalent to 12 ounces of regular beer, 8 to 9 ounces of malt liquor, 5 ounces of wine, or 1.5 ounces of 80 proof distilled spirits.

Subjects must abstain from alcohol consumption within 48 hours prior to each visit (including screening).

Subjects must not use of any nicotine or tobacco containing products throughout the study. These types of products include but are not limited to: snuff, chewing tobacco, cigars, cigarettes, pipes, electronic cigarettes, or nicotine patches.

6.3.2 Activity

In the phase 1b part of the study subjects will abstain from strenuous exercise for 72 hours (eg, running, weight lifting for greater than 1 hour) before each blood collection for clinical laboratory tests.

6.4 Subject Enrollment

Before subjects begin participation in any study-specific activities/procedures, Amgen requires a copy of the site's written institutional review board/independent ethics committee (IRB/IEC) approval of the protocol, informed consent form, and all other subject information and/or recruitment material, if applicable (see [Appendix 3](#)).

The subject must personally sign and date the IRB/IEC and Amgen approved informed consent before commencement of study-specific procedures.

A subject is considered enrolled when the investigator decides that the subject has met all eligibility criteria. The investigator is to document this decision and date, in the subject's medical record and in/on the enrollment case report form (CRF).

Each subject who enters into the screening period for the study defined as the point at which the subject signs the informed consent form receives a unique subject identification number before any study-related activities/procedures are performed. The subject identification number will be assigned by IVRS. This number will be used to identify the subject throughout the clinical study and must be used on all study documentation related to that subject.

The subject identification number must remain constant throughout the entire clinical study; it must not be changed after initial assignment, including if a subject is rescreened. This number will not necessarily be the same as the randomization number assigned for the study.

6.5 Screen Failures

Screen failures are defined as subjects who consent to participate in the clinical study but are not subsequently enrolled in the study. A minimal set of screen failure

information will be collected that includes demography, screen failure details, eligibility criteria, and any serious adverse events.

Individuals who do not meet the criteria for participation in this study (screen failure) may be rescreened ([Section 9.1.1](#)).

7. Treatments

Study treatment is defined as any investigational product(s), non-investigational product(s), placebo, or medical device(s) intended to be administered to a study subject according to the study protocol.

Note that in several countries, investigational product and non-investigational product are referred to as investigational medicinal product and non-investigational medicinal product, respectively.

The Investigational Product Instruction Manual (IPIM), a document external to this protocol, contains detailed information regarding the storage, preparation, destruction, and administration of investigational product.

7.1 Treatment Procedures

7.1.1 Investigational Products

[figure not shown]
7.1.1.1 Amgen Investigational Product: AMG 592

AMG 592 and placebo will be manufactured and packaged by Amgen Inc. and distributed using Amgen clinical study drug distribution procedures.

[figure not shown]
Both are liquid formulations presented in highly similar glass vials and stored in the same manner. An investigational product instruction manual (IPIM) containing detailed information regarding the storage, preparation, and administration of investigational product will be provided separately.

7.1.1.1.1 Dosage Administration and Schedule

In the phase 1b part of the study, AMG 592 or placebo will be administered by SC injection [REDACTED] starting on day 1. The following dose cohorts are planned in the phase 1b portion of the study:

[figure not shown]

Approved

For both the phase 1b and phase 2a part of the study investigational product will be administered by SC injection in the abdomen, thigh or upper arm by authorized site personnel. A physician must be available at the time of investigational product administration.

In the phase 1b part of the study doses of investigational product through week 4 and during week 12, must be given within 1 hour after the specified time point for the day 1 pre-dose blood samples, and within 12 hours after the rest of scheduled pre-dose blood sampling time points. After week 4 (excluding week 12) doses of investigational product must be given within ± 1 day of the scheduled visit time point. If that window is missed, that dose will not be administered, and the next dose will be administered at the next scheduled dosing date.

In the phase 1b part of the study, study subjects must remain at the site at least 6 hours following the first dose and at least 1 hour following the second dose of investigational product. The site must contact the subject by phone 6, 12, and 24 hours after the second dose of study drug to ascertain safety. Thereafter study subjects must remain on site for at least 30 minutes following the third and all subsequent doses of investigational product.

7.1.1.1.2 Accountability

The amount of investigational product used in preparation, total volume of preparation, quantity administered, start date, start time, and box number of AMG 592 are to be recorded on each subject's CRF.

7.1.2 Non-investigational Products

There are no therapies designated as non-investigational products in the study.

7.1.3 Medical Devices

There are no investigational medical device(s) used in this study.

Approved

Other non-investigational medical devices may be used in the conduct of this study as part of standard care.

Non-investigational medical devices (eg, syringes, sterile needles), that are commercially available are not usually provided or reimbursed by Amgen (except, for example, if required by local regulation). The investigator will be responsible for obtaining supplies of these devices.

7.1.4 Other Protocol-required Therapies

There are no other protocol required therapies

7.1.5 Other Treatment Procedures

There are no other treatment procedures

7.1.6 Product Complaints

A product complaint is any written, electronic or oral communication that alleges deficiencies related to the identity, quality, durability, reliability, safety, effectiveness, or performance of a drug(s) or device(s) after it is released for distribution to market or clinic by either Amgen or by distributors and partners for whom Amgen manufactures the material.

This includes any drug(s), device(s) or combination product(s) provisioned and/or repackaged/modified by Amgen. Drug(s) or device(s) includes investigational product.

Amgen will collect product complaints in this study for investigational product.

Any product complaint(s) associated with an investigational product(s), non-investigational product(s), device(s), or combination product(s) supplied by Amgen are to be reported according to the instructions provided in the IPIM.

[figure not shown]
7.1.7 Excluded Treatments, Medical Devices, and/or Procedures During Study Period

The following medications are not allowed at any time during the study:

- azathioprine
- gold
- mycophenolate mofetil
- Prosorba column
- Any other investigational agents or commercially available biologic DMARDs
- Cytotoxic agents including chlorambucil, cyclophosphamide, nitrogen mustard, or other alkylating agents
- oral janus kinase inhibitor (eg, tofacitinib, baricitinib)

[figure not shown]
- Live vaccines
- Tacrolimus
- Cyclosporine
- T cell depleting agents (eg, antithymocyte globulin, Campath)
- Recombinant IL-2 (eg, Proleukin)

During the phase 1b part of the study all herbal medicines (eg St John's wort), vitamins, and supplements are not allowed, with the exception of Vitamin D and calcium.

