3.2.3 Low Dose Interleukin 2 in Inflammatory Disease

Low dose IL-2 (aldesleukin) has been shown to increase Treg numbers in multiple inflammatory diseases such as systemic lupus erythematosus ([SLE] [Humrich et al, 2015](#)), Type 1 Diabetes ([Yu et al, 2015](#)), chronic graft versus host disease ([GVHD] [Koreth et al, 2011](#)), hepatitis c virus induced vasculitis ([Sadoun et al, 2011](#)) and alopecia areata ([Castela et al, 2014](#)) as well as to correct defects in Treg function in SLE ([von Spee-Mayer et al, 2015](#)), Type 1 Diabetes ([Long et al, 2010](#); [Long et al, 2012](#)) and GVHD ([Matsuoka et al, 2013](#)). Genetic variants of the IL-2 receptor have been associated with the severity of RA joint destruction and persistence ([van Steenbergen et al, 2015](#)).

[figure not shown]
The therapeutic efficacy of low dose IL-2 has been studied in chronic GVHD ([Koreth et al, 2011](#); [Koreth et al, 2016](#)), hepatitis C induced vasculitis ([Sadoun et al, 2011](#)), SLE ([Humrich et al, 2015](#)), and alopecia areata ([Castela et al, 2014](#)). The clinical response to low dose IL-2 has been promising in these small early phase studies in multiple diverse inflammatory conditions. In all of these conditions the overall safety and tolerability profile of low-dose IL-2 has been acceptable with mild to moderate constitutional symptoms associated with higher levels of exposure. However, the therapeutic window between adequate Treg enrichment and stimulation of effector cells is narrow and may limit achievement of optimal Treg expansion. For instance, in a recent Phase 1b clinical trial of chronic GVHD (ClinicalTrials.gov NCT00529035), an IL-2 dose of 3×10^6 IU/m² daily induced persistent National Cancer Institute Common Terminology Criteria for Adverse Events (CTCAE) grade 1 constitutional symptoms (fever, malaise, and arthralgia) necessitating a 50% dose reduction ([Koreth et al, 2011](#)). In addition adesleukin can activate

pro-inflammatory/effector lymphocytes such as CD4+ T effector cells (Teff) and natural killer (NK) cells, which may compromise efficacy and safety.

These data suggest the potential for a therapeutic agent with greater Treg selectivity and a prolonged PD effect compared with IL-2.

Approved

Approved

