4.1 Objectives and Endpoints

[figure not shown]
| Objectives | Endpoints |
|---|--|
| Primary | |
| Phase 1b 
 To evaluate the safety and tolerability of subcutaneous (SC) dose administrations of AMG 592 in subjects with active RA | Phase 1b 
 Treatment-emergent adverse events. Clinically significant changes in vital signs, laboratory safety tests, and electrocardiograms (ECGs) |
| Phase 2a 
 To evaluate the efficacy of AMG 592 at week 12 as measured by the American College of Rheumatology 20% improvement criteria (ACR 20) in adult subjects with moderate to severe RA | Phase 2a 
 ACR 20 at week 12 |
| Secondary | |
| Phase 1b 
 To characterize the pharmacokinetic (PK) profile following treatment with AMG 592 | Phase 1b 
 AMG 592 serum concentration and PK parameters including, but not limited to, maximum observed concentration (C_{max}), the time of maximum observed concentration (T_{max}), and area under the concentration-time curve (AUC_{tau}) after the first and last doses. Area under the concentration-time curve over the dosing interval will be calculated & reported for each dosing regimen |
| 
 To evaluate the incidence of anti-AMG 592 antibody formation and cross-reactivity to human IL-2. | 
 Anti-AMG 592 antibodies and cross-reactivity to IL-2. Anti-AMG 592 and anti-IL 2 neutralizing antibodies |
| Phase 2a 
 To evaluate the effect of treatment with AMG 592 on other measures of disease activity at week 12 | Phase 2a 
 ACR 50/70 at weeks 12 Disease activity score (28 joint) calculated using the erythrocyte sedimentation rate |

Approved

| Objectives | Endpoints |
|---|---|
| | formula (DAS28-ESR) score and change from baseline at week 12 
• Disease activity score (28 joint) calculated using the C-reactive protein formula (DAS28-CRP) score and change from baseline at week 12 |
| 
• To evaluate the safety of AMG 592 | 
• Treatment-emergent adverse events.• Clinically significant changes in vital signs, laboratory safety tests |

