- 210 Presence of one or more significant concurrent medical conditions per investigator judgment, including but not limited to the following:
- poorly controlled diabetes or hypertension
 - chronic kidney disease stage IIIb, IV, or V
 - symptomatic heart failure (New York Heart Association class II, III, or IV)
 - myocardial infarction or unstable angina pectoris within the past 12 months prior to randomization
 - severe chronic pulmonary disease (eg, requiring oxygen therapy)
 - multiple sclerosis or any other demyelinating disease
 - major chronic inflammatory disease or connective tissue disease other than RA (eg, systemic lupus erythematosus with the exception of secondary Sjögren's syndrome)
- 211 Malignancy except non-melanoma skin cancers, cervical or breast ductal carcinoma in situ within the last 5 years.
- 212 History of alcohol or substance abuse within 6 months of screening
- 213 Phase 1b only: Current smoker, and/or use of any nicotine or tobacco containing products within the last 6 months prior to day 1. These types of products include but are not limited to: snuff, chewing tobacco, cigars, electronic cigarettes, cigarettes, pipes, or nicotine patches.
- 214 Phase 1b only: Subject unwilling to limit alcohol consumption to ≤ 1 drink of alcohol per day and ≤ 3 drinks per week for the duration of the study, where a drink is equivalent to 12 ounces of regular beer, 8 to 9 ounces of malt liquor, 5 ounces of wine, or 1.5 ounces of 80 proof distilled spirits. Phase 1b only: Unwilling or unable to abstain from alcohol consumption within 48 hours prior to each visit (including screening).

Prior/Concomitant Therapy

- 215 Subjects who have received intra-articular or systemic corticosteroid injections for treatment of acute RA flare (not being part of a regular therapeutic regimen) within 4 weeks prior to screening.
- 216 Currently receiving or had treatment with cyclophosphamide, chlorambucil, nitrogen mustard, or any other alkylating agent ≤ 6 months prior to day 1.
- 217 Prior treatment with more than a total of 3 therapies that include biologic DMARDs or oral synthetic DMARDs (such as tofacitinib, baricitinib). Prior treatment consists of at least 4 doses of a given therapy where the doses were given solely for treatment of RA disease. Prior therapies must not have been used within the following time periods:
- ≤ 4 weeks prior to day 1 for etanercept and anakinra
 - ≤ 6 months for rituximab
 - ≤ 2 weeks for oral janus kinase inhibitors

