 - ≤ 9 weeks prior to day 1 for all therapies not listed above

Approved

- 218 Currently receiving or had treatment with any of the following \leq 12 weeks prior to day 1:
- azathioprine
 - cyclosporine
 - gold
 - mycophenolate mofetil
 - ProSORBA column
 - Tacrolimus
- 219 Phase 2a only: Currently receiving or had treatment with leflunomide \leq 12 weeks prior to day 1 unless an active washout with cholestyramine has been performed.
- 220 Phase 2a only: Currently receiving or had treatment with any of the following \leq 4 weeks prior to day 1:
- hydroxychloroquine
 - sulfasalazine
 - minocycline
 - intra-articular, intramuscular or intravenous corticosteroids, including adrenocorticotrophic hormone
 - intra-articular hyaluronic acid injections
 - live vaccines
- 221 For Phase 2 only: Unstable dose of non-steroidal anti-inflammatory drugs (NSAID), acetaminophen, and/or analgesics which is taken on an unscheduled basis (ie, not daily or scheduled every certain number of hours) and/or initiated $<$ 4 weeks prior to day 1.
- 222 Received the following within 12 hours prior to screening or day 1: acetaminophen, NSAIDs, tramadol, and/or any narcotic analgesics such as but not limited to hydrocodone, codeine, tramadol, propoxyphene and/or oxycodone (unless in the form of oxycontin). Subject has taken oxycontin within 24 hours prior to screening or day 1.
- 223 Phase 1b only: Received any herbal medicines (eg, St John's wort), or non-vitamin dietary supplements (eg, magnesium) with the exception of calcium within 4 weeks prior to day 1.

Prior/Concurrent Clinical Study Experience

- 224 Currently receiving treatment in another investigational device or drug study, or less than 30 days since ending treatment on another investigational device or drug study(ies). Other investigational procedures while participating in this study are excluded.

Diagnostic Assessments

- 225 Presence of laboratory abnormalities at screening including the following:
- Aspartate aminotransferase (AST) or alanine amino transferase (ALT) at screening $>$ 1.5X upper limit of normal (ULN)

- Serum total bilirubin (TBL) ≥ 1.5 mg/dL (≥ 26 $\mu\text{mol/L}$)
- Hemoglobin ≤ 10.5 g/dL (≤ 105 g/L)
- Platelet count $< 100,000/\text{mm}^3$ ($< 100 \times 10^9/\text{L}$)
- White blood cell count $< 2,500$ cells/ mm^3 ($< 2.5 \times 10^9/\text{L}$)
- Absolute neutrophil count (ANC) $< 1,000/\text{mm}^3$ ($< 1.0 \times 10^9/\text{L}$)

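### Phase 1b has no pre-day 1 exclusion for three treatments that are banned on study (live vaccines, T-cell-depleting agents, recombinant IL-2); live vaccines are the clearest gap

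*Protocol*

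**What the plan says.** Protocol section 7.1.7 opens with "The following medications are not allowed at any time during the study" and sets no phase limit on the list that follows. The list has twelve entries, among them "Live vaccines", "T cell depleting agents (eg, antithymocyte globulin, Campath" and "Recombinant IL-2 (eg, Proleukin".

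In section 6.2, live vaccines appear once, as the last entry of criterion 220. That criterion begins "Phase 2a only: Currently receiving or had treatment with any of the following" and looks back 4 weeks from day 1. T-cell-depleting agents and recombinant IL-2 are named in no criterion.

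Two sections bear on timing. Section 5.3.2 counts screening, of up to 28 days, as part of the phase 1b study. Section 9.1.1 repeats the 28-day maximum and sets no minimum. Section 6 rules out eligibility waivers, so the criteria apply as written.

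On outcomes, section 3.2.3 says that low-dose IL-2 "has been shown to increase Treg numbers in multiple inflammatory diseases", and the phase 1b secondary endpoints in section 4.1 include "Anti-AMG 592 and anti-IL 2 neutralizing antibodies".

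**The concern.** An on-study ban is usually paired with a look-back before first dose, because an exposure shortly before day 1 can act during treatment much as one shortly after it would. Section 6.2 follows that pattern for most of the 7.1.7 list. Where the pair is missing, a subject can enter with a recent exposure that the protocol would not tolerate a few weeks later.

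Phase 1b is a small dose-escalation study whose primary endpoint is safety. A vaccine reaction that appears after first dose would enter the adverse event tables and could interrupt a cohort. Recent T-cell depletion or IL-2 treatment could shift the T-cell pharmacodynamic baseline or the anti-IL-2 antibody results. SAP sections 4.1.1 and 4.2.1 specify no covariates or subgroups for phase 1b, so no planned analysis would separate such a subject out.

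**Working it through.** No figure in the plan bears on this point, so the check sets the two lists side by side and then works through timing and weight.

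**1. Each 7.1.7 entry against a pre-day 1 rule that applies to phase 1b**

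| 7.1.7 entries | Rule in 6.2 for phase 1b |
|---|---|
| Azathioprine, cyclosporine, gold, mycophenolate mofetil, Prosorba column, tacrolimus (6 entries) | 218 |
| Alkylating and other cytotoxic agents (1) | 216 |
| Biologic DMARDs and investigational agents (1) | 217, 224 |
| Oral JAK inhibitors (1) | 217 |
| Live vaccines (1) | none; 220 is limited to phase 2a |
| T-cell-depleting agents (1) | none by name |
| Recombinant IL-2 (1) | none by name |

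Nine entries (6 + 1 + 1 + 1) are paired and three are not; 9 + 3 = 12.

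**2. Is the phase limit in criterion 220 explained by its other entries?** Hydroxychloroquine, sulfasalazine and minocycline are allowed at a stable dose in phase 1b by criterion 107, so limiting those entries to phase 2a makes sense. Injected corticosteroids and hyaluronic acid are not on the 7.1.7 list. Live vaccines are the only entry in 220 that 7.1.7 also bans.

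**3. Do other criteria close the gap?**
- 217 opens with "Prior treatment with more than a total of 3 therapies that include biologic DMARDs or oral synthetic DMARDs" and counts a therapy as prior treatment only after at least 4 doses given for RA alone. Its 9-week default sits under that definition.
- 224 covers treatment in another investigational study that is current or ended less than 30 days earlier.
- 211 works through a malignancy history, not through the drug received.
- 226 (other laboratory abnormalities) and 232 (other disorders or conditions) depend on opinion. Neither is a drug-exposure rule.

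These can catch some subjects exposed to T-cell-depleting agents or IL-2. They offer little against a recent live vaccine in a subject who is otherwise well.

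**4. Timing.** Let s be the days from consent to day 1 and d (at least 1) the days from vaccination to consent. The vaccine was then given s + d days before day 1. In phase 2a, criterion 220 excludes the subject when s + d ≤ 28; in phase 1b nothing does. Using 220's own look-back purely as a yardstick, the uncovered exposures are d = 1 to 28 − s:
- s = 7 (illustrative): 28 − 7 = 21 days before consent
- s = 14 (illustrative): 28 − 14 = 14 days
- s = 28 (the maximum): 28 − 28 = 0 days

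This assumes that the 7.1.7 ban runs from consent. If it runs only from day 1, the whole 28 days is uncovered whatever s is. The text does not settle this. Section 5.3.2 puts screening inside the study, whereas section 9.1.1 requires consent before a disallowed therapy is stopped, which implies that a subject may still be taking one at consent.

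**5. What an event would do.** SAP section 5.3 defines an event as treatment-emergent by its start date, whatever its cause. In Protocol Table 7-1, any event of Grade 4 or higher stops dosing of additional subjects in the cohort and convenes the dose level review meeting, which then considers relatedness.

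**6. Weight of one subject on AMG 592.** Cohort 1 or 4: 1/6 = 16.7%. Cohort 2 or 3 as expanded: 1/12 = 8.3%. All planned AMG 592 subjects: 1/36 = 2.8%.

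**The case against.** A reader might infer that anyone given one of these agents just before first dose is eligible and confounds the results. The documents do not support that.

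- **Eligibility.** An agent given between consent and day 1 arguably breaches 7.1.7, since screening is part of the study. The firm gap is exposure before consent followed by short screening, although 7.1.7 is not itself an eligibility test.
- **The two other agents.** Criterion 226, read with the lymphocyte count in screening hematology, could remove a subject with marked T-cell depletion. The low-dose IL-2 efficacy studies described in section 3.2.3 were small, early-phase and not in RA. Criterion 224 excludes recent study treatment, and criteria 207 and 210 exclude detectable hepatitis C RNA and SLE.
- **Confounding.** It is possible but not shown. Phase 1b is randomized and placebo-controlled, an antibody sample is taken before the first dose, and section 7.8.1 collects therapies from 6 months before it. The pharmacodynamic endpoints are largely redacted, so the effect on Treg results cannot be checked.
- **Cohort stopping.** A reader might count one vaccinated subject as half of the two needed for the Grade 3 rule. That rule requires events deemed related, and Appendix 4 tells investigators to weigh alternative causes. The Grade 4 rule acts sooner, but the review meeting can resume enrollment, and the table's footnote ties a decision to stop dosing to unblinding.
- **Allocation.** The 16.7% and 8.3% apply only to a subject on AMG 592. Under 3:1 randomization, one in four would be on placebo.

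It is also fair to say that an on-study ban and a prior-therapy exclusion are different rules, so 6.2 and 7.1.7 do not contradict each other, and that the two parts differ on purpose elsewhere.

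These points narrow the concern and make it mainly one about live vaccines. They do not supply the missing phase 1b rule. Criterion 110 also makes vaccination near screening foreseeable: it asks for immunizations to be up to date and does not address live products.

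**Conclusion.** The point holds in a limited form. For phase 1b, three of the twelve entries banned by 7.1.7 have no named exclusion before day 1. For live vaccines the cause is visible: the only rule is confined to phase 2a, and no other entry in that criterion is also on the 7.1.7 list. A recently vaccinated phase 1b subject can therefore be dosed without breaking any listed criterion.

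For T-cell-depleting agents and recombinant IL-2 the omission covers both parts. Exposure before consent could affect T-cell pharmacodynamic and anti-IL-2 antibody results, but partial cover exists and such exposure is probably rare in this population.

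The documents give no exposure frequency, so the expected number of affected subjects cannot be estimated. The size is therefore the weight of a single subject, together with a possible temporary stop to dosing additional subjects in the cohort. No sample size or analysis figure changes.

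The conclusion assumes that no redacted text holds a further criterion (the exclusions run from 201 to 232 without a break) and that the discretionary criteria are not used as an unwritten vaccine rule.

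**What to change.** Reconcile sections 6.2 and 7.1.7 in the next amendment:

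1. Either remove the phase 2a limit on live vaccines in criterion 220 or state why it is intended.
2. Have the sponsor decide, for both parts, whether T-cell-depleting agents and recombinant IL-2 need a prior-therapy exclusion. Any window is for the sponsor to set; none is proposed here.
3. State in 7.1.7 whether the ban starts at consent or at day 1, and make section 9.1.1 agree with it.

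The cost is a few lines of eligibility wording. The downside is that an occasional subject is excluded or has day 1 delayed. The statistical analysis does not change.
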